Thoughtful specification of the prior distribution is crucial in Bayesian analysis. We want conclusions to depend primarily on data from the trial, not on prior opinion. This argues for a skeptical prior distribution that does not already assume that a treatment works. Let p denote the probability of survival in a given arm. Our prior distribution on p can be formulated by imagining having data on 2 people treated with a given agent, and observing that exactly 1 of the 2 survived. The probabilistic equivalent is to assume a beta prior distribution on p with parameters 1 and 1, equivalent to a uniform distribution on the interval (0,1). This is consistent with an overall survival probability of 0.50 for the current Ebola outbreak, but with wide variability reflecting substantial uncertainty about p. Moreover, a uniform distribution for p ensures very little influence of our prior opinion on conclusions. The observed data very quickly dominate in decision-making. For instance, if 20 people are given the treatment and 12 of them survive, the posterior distribution for the survival probability is beta with parameters 13 and 9. In other words, combining our prior opinion with the observed data equates to observing 13+9=22 people, 13 of whom survived. Our prior opinion constitutes only 2 of the 22

people, and therefore has very little effect on the conclusions. Also, we use the same prior distribution in different arms. That way, our prior opinion does not favor any treatment over oSOC. If p_A and p_B denote the survival probabilities in arms A and B, respectively, we use independent beta posterior distributions in the 2 arms to calculate the probability that $p_A < p_B$, namely that the survival probability in arm B exceeds that in arm A. At any interim analysis preceding the final analysis, we declare arm B superior if this probability exceeds 99.9%. At the final analysis, we declare superiority of arm B if this probability exceeds 97.5%.

Analyses

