Differences in mortality probabilities between an experimental arm and the best supportive care arm will be estimated using 95% Bayesian credibility intervals akin to confidence intervals. The treatment effect will be expressed in both an absolute and relative terms, and will be estimated in the overall group and in the pre-defined strata: baseline threshold cycle (CT) value on PCR (≤ 22 versus > 22) and where the patient was treated (western Africa versus the United States/Europe). The posterior probability that the relative treatment benefit differs by strata will be calculated; if this probability exceeds 97.5% that will be taken as evidence of a differential treatment effect by strata.

As noted earlier, Bayesian analysis with the non-informative prior distribution specified above is very similar to classical statistical analysis using Barnard's test. To highlight this point, we will also present classical confidence intervals for the absolute and relative treatment benefit based on Barnard's test.

Some patients may receive MCMs other than the randomized treatment. This will be documented in the record, but it is extremely problematic statistically to try to account for the effect of supplementary treatment that may be administered in response to a patient's failing health. A sensitivity analysis will be conducted by treating such patients as if they would have died by 28 days in the absence of the additional MCMs.

Similar sensitivity analyses will be conducted for patients missing the primary endpoint of 28 day mortality.

The analyses of the symptom histories obtained in extended follow-up of patient are intended to be observational and descriptive in nature, will apply to patients in all treatment arms, and are designed to provide some additional information as to whether there is a detectable increase in delayed virologic relapse in trial participants over a period of one year or more following recovery and initial clearance of virus from the plasma.

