4.4.2 Additional analyses

4.4.2.1 STRATIFIED ANALYSIS

In addition to the above grouped summaries, we will also complete a stratified analysis by the location of treatment (West Africa vs. U.S.) and CT value (> 22 vs. \leq 22). Stratified analyses will be completed separately for the two stratification factors and will be completed once data are available for the two stratum. Analyses will be completed assuming the Bayesian paradigm with uniform(1,1) prior distributions for the 28-day mortality rate in each stratum. The following summaries of the stratified analyses will be reported:

- 1. Basic summaries of 28-day survival (N and %) for each group within a stratum, broken down into the following categories: dead, alive and still in follow-up period.
- 2. Point estimate and 99.8% credible interval for the relative risk of 28-day mortality between the two treatment arms for each stratum.
- 3. The posterior probability that the relative risk in stratum 1 is greater than the relative risk in stratum 2. The relative risks will be considered significantly different if the posterior probability is greater than 0.975 or less than 0.025.

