3.8 Primary Outcome

The primary outcome is death within 28 days from randomization, and the primary population includes all randomized patients, with the exception of one individual who fled from the ETU on the first day and for whom no other primary data were subsequently captured.

Note: as a sensitivity analysis to assess the impact of the single subject with unknown vital status following randomization, the primary analysis described below will be performed assuming the subject was alive at 28 days and repeated assuming the subject was dead at 28 days.

Primary analysis

Inference relating to the primary endpoint will quantify the probability that the 28-day mortality rate is lower (or higher) under ZMapp relative to oSOC using the Bayesian paradigm as follows:

- A. The prior distribution of 28-day mortality probabilities, p₀ and p₁, in the oSOC and ZMapp arms is that of independent uniforms on [0,1].
- B. The posterior distributions of p₀ and p₁ after observing x₀ and x₁ deaths among n₀ and n₁ people in the two arms is that of independent betas with respective parameters (x₀+1, n₀-x₀+1) and (x₁+1, n₁-x₁+1).
- C. The posterior probability that p₁<p₀ will be computed: if this probability is 0.975 or greater, ZMapp will be declared superior to oSOC, whereas if the probability is 0.025 or less, ZMapp will be declared inferior to oSOC.
- D. Treatment effect estimates and 95% credible intervals will be computed for both the relative risk p_1/p_0 and absolute risk difference p_1-p_0 . The medians of the posterior distributions of p_1/p_0 and p_1-p_0 are used to estimate these quantities. 95% credible intervals are computed as follows.
 - a. For p_1/p_0 , compute lower and upper limits (L and U, respectively) satisfying $P(p_1/p_0 \le L \text{ given } x_0, x_1) = 0.025$ and $P(p_1/p_0 \ge U \text{ given } x_0, x_1) = 0.025$.
 - b. For p₁-p₀, compute lower and upper limits (L and U, respectively) satisfying P(p₁-p₀<L given x₀,x₁)=0.025 and P(p₁-p₀>U given x₀,x₁)=0.025.

Additional Supportive Analyses Using Primary Outcome:

Alternative test statistics:

The following alternative test statistics will be performed on the primary outcome as secondary analyses.

- Barnard's unconditional test will be performed using a one-tailed test of p₁=p₀ versus p₁<p₀.
 - A. The first alpha level used is 0.025 (one-sided). As with the Bayesian analysis, the overall type 1 error rate including monitoring may exceed 0.025.

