 - B. The second alpha level is adjusted using the Haybittle-Peto monitoring procedure:

 α =0.025-(0.001)k, where k is the number of interim looks at the data.

A confidence interval will be computed for the absolute risk difference using Barnard test methodology and confidence level $1-2\alpha$. This will be done for each of the two alpha levels specified above.

- The same approach specified above for Barnard's test, including the two separate alpha levels, will also be performed for Fisher's exact test. A confidence interval for the odds ratio will be computed using the non-central hypergeometric distribution.
- An analysis of time to death will be performed using a log-rank test. In addition, a stratified log-rank test will be performed with 4 strata defined by location and cycle threshold. (See description of stratification variables below). This will be done for each of the two alpha levels specified above. Tests of treatment by subgroup interaction will be performed.

Stratification and subgroup analyses

- Additional analyses will be performed within two strata defined by cycle threshold: ≤22 versus >22 for all subjects. To assess whether there is a treatment by cycle threshold interaction, we will compute the posterior probability that the treatment effect (absolute or relative) differs by cycle threshold.
- Analysis combining the United States, Liberia, and Sierra Leone as one location stratum, while Guinea constitutes the other location stratum. (The standard of care in Guinea typically included favipiravir, which was not the case in the other countries). Note that the protocol initially specified stratified randomization for the USA. However, only one patient in the USA was randomized, which is why the location strata have been changed to USA/Liberia/Sierra Leone vs Guinea. To assess whether there is a treatment by location interaction, we will compute the posterior probability that the treatment effect (absolute or relative) differs by location. An additional sensitivity analysis will exclude the lone patient treated in the United States. The treatment effect within the United States versus West Africa could make interpretation of results more difficult. For example, if the patient was assigned to oSOC and survived, that may simply reflect better oSOC in the United States.

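### Protocol section 22 judges effect modification by a posterior probability that is always 1, and the Final Data Analysis Plan leaves the same quantity without a direction, a single scale or a cut-off

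*Combined protocol and SAP*

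**What the plan says.** Three texts deal with whether the effect on 28-day mortality varies by stratum.

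- **Protocol, section 22, Analyses** (same wording in section 7 of the earlier protocol version): "The posterior probability that the relative treatment benefit differs by strata will be calculated", and "if this probability exceeds 97.5% that will be taken as evidence of a differential treatment effect by strata". The scale is relative. No direction is given.
- **MCM RCT Data Analysis Plan, 4.4.2.1**: the quantity is "The posterior probability that the relative risk in stratum 1 is greater than the relative risk in stratum 2", and "The relative risks will be considered significantly different if the posterior probability is greater than 0.975 or less than 0.025". The factors are cycle threshold (CT) and West Africa versus U.S.
- **Final Data Analysis Plan (January 20, 2016), 3.8**: for CT, "we will compute the posterior probability that the treatment effect (absolute or relative) differs by cycle threshold"; for location, "we will compute the posterior probability that the treatment effect (absolute or relative) differs by location". No cut-off is attached to either. The location factor is now USA/Liberia/Sierra Leone versus Guinea, because favipiravir was usually part of standard care in Guinea. Other subgroup analyses (age, symptom duration, baseline risk score) are to follow the same strategies.

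The priors are uniform on 0 to 1. In Final Data Analysis Plan 3.8 the posterior "is that of independent betas with respective parameters" determined by the deaths and survivors in each arm.

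**The concern.** A posterior probability that two quantities *differ* carries information only if the prior gives some weight to exact equality. These priors give none. The probability in section 22 is then fixed in advance, and comparing it with 97.5% is not a test of anything.

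The Final Data Analysis Plan covers the key analyses for publication. There the same quantity appears without a direction or a cut-off, and with a choice of two scales. An analyst would have to decide after unblinding what to compute, on which scale, and what counts as a finding. At stake are statements that ZMapp works differently by viral load, by location (and so by background favipiravir), or by baseline risk.

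**Working it through.** **1. Check of the method against the plan's own figures.** The documents give no operating characteristics for the interaction rule, so the check uses the primary comparison. Inputs: Beta(1,1) priors; looks at 6 to 20, then 40, 60, 80 and 100 per arm; cut-offs 0.999 interim and 0.975 final, either direction (section 22). With 40,000 simulated trials at 100 per arm:

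| True mortality | Table 11 | Recomputed |
|---|---|---|
| 0.3 v 0.5 (power) | 0.83 | 0.835 |
| 0.2 v 0.4 (power) | 0.88 | 0.880 |
| 0.5 v 0.5 (type I error) | 0.063 | 0.063 |

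The Table 10 boundaries checked also match. At 6 per arm, (6,0) gives 0.9997 and (5,0) gives 0.9977, so only (6,0) passes 0.999.

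**2. The literal rule.** Let RR1 and RR2 be the mortality relative risks in the two strata, formed from four independent beta posteriors. Given three of the four mortality probabilities, RR1 = RR2 only if the fourth takes one exact value, which has probability 0. So

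P(RR1 ≠ RR2 | data) = 1 − P(RR1 = RR2 | data) = 1 − 0 = 1.

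The same holds for risk differences (RD). Two examples with 18 patients per arm per stratum:

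| Deaths, stratum 1 (ZMapp, oSOC) | Deaths, stratum 2 (ZMapp, oSOC) | P(RR1 ≠ RR2) | P(RR1 > RR2) |
|---|---|---|---|
| 6, 6 | 6, 6 | 1.000 | 0.50 |
| 6, 10 | 1, 3 | 1.000 | 0.63 |

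Identical data in both strata still give 1.000. The directional probability gives 0.50, as it should.

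**3. The directional rule of 4.4.2.1.** Each setting had 3,000 simulated trials with 4,000 posterior draws each. Stratum sizes and mortalities are assumptions. Sizes of 18 and 18, or 15 and 21, per arm total 72 patients (4 × 18; 2 × 15 + 2 × 21), the number the Final Data Analysis Plan reports as randomized by January 14, 2016. Sizes of 50 and 50 total the planned maximum of 200. *Two-sided* means above 0.975 or below 0.025; *one-sided* means above 0.975 only.

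| Per arm, strata 1 and 2 | True mortality | RR, two-sided | RR, one-sided | RD, two-sided |
|---|---|---|---|---|
| 18, 18 | 0.37 everywhere | 4.4% | 2.4% | 5.1% |
| 18, 18 | 0.60 and 0.15, no effect | 3.2% | 1.8% | 3.8% |
| 18, 18 | RR 0.5; oSOC 0.60 and 0.20 | 3.8% | 1.0% | 14.9% |
| 15, 21 | 0.37 everywhere | 4.4% | 2.0% | 4.9% |
| 15, 21 | 0.60 and 0.15, no effect | 3.8% | 1.7% | 3.9% |
| 15, 21 | RR 0.5; oSOC 0.60 and 0.20 | 3.6% | 1.0% | 13.3% |
| 50, 50 | 0.37 everywhere | 4.9% | 2.3% | 5.7% |
| 50, 50 | 0.60 and 0.15, no effect | 4.4% | 2.3% | 3.6% |
| 50, 50 | RR 0.5; oSOC 0.60 and 0.20 | 4.6% | 1.7% | 37.8% |

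The literal rule fired in 100% of trials in every row. True RRs are equal throughout, so the two-sided RR column (3.2% to 4.9%) is a false-positive rate. The simulation standard error near 4% is √(0.04 × 0.96 / 3,000), about 0.4 points.

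**4. Why the scale matters.** In the RR 0.5 rows the true risk differences are 0.30 − 0.60 = −0.30 and 0.10 − 0.20 = −0.10. The absolute effects really do differ, so the same data can be called homogeneous on one scale and heterogeneous on the other.

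**The case against.** The strongest reply is that nobody would program the literal rule. Wherever else the documents use 0.975, it goes with a directional probability, and 4.4.2.1 spells out the intended quantity. That is a fair account of what was probably meant, and it makes this a defect of specification rather than of method.

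It does not close the point. One-sided and two-sided readings of section 22 are both possible and fire at different rates (1.0% to 2.4% against 3.2% to 4.9%). The definition in 4.4.2.1 belongs to the closed report to the DSMB, in a plan that the Final Data Analysis Plan updates, and it never covered the Guinea split. The later plan restates the primary rule with a direction and two cut-offs, but not the interaction rule.

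Three stronger readings are tempting, and the documents do not support them.

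- *The Final Data Analysis Plan would always declare effect modification.* It repeats the undirected quantity but not the 97.5% cut-off, so as written it declares nothing. The 100% rate belongs only to the literal protocol rule.
- *All claims about CT and location depend on this rule.* Section 3.8 also plans interaction tests alongside the log-rank analyses, and separate tests by location and CT alongside the Mantel-Haenszel analysis.
- *The high absolute-scale rates are false positives.* They are detection of real differences in risk difference under assumed mortalities. With no treatment effect, the absolute-scale rule fires in 3.6% to 5.7% of trials.

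**Conclusion.** Wrong as written, and limited in reach. The protocol's interaction rule is satisfied by any data set; this follows from the continuous posteriors and needs no assumption about the results. The Final Data Analysis Plan leaves the quantity undirected, allows either scale and sets no cut-off for CT or the new location split, and it extends the approach to other subgroups. The sponsor's own directional rule behaves properly, with about 3% to 5% false positives when the true relative risks are equal. That range rests on the assumed stratum sizes and mortalities above. The consequence is confined to supportive subgroup claims. The primary analysis is untouched, and so are the separate interaction tests in 3.8.

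**What to change.** In protocol section 22 and Final Data Analysis Plan 3.8, replace the undirected probability with P(RR in stratum 1 > RR in stratum 2). Declare a differential effect only if it is above 0.975 or below 0.025. Name the current strata: CT ≤22 versus >22, and USA/Liberia/Sierra Leone versus Guinea. Keep relative risk as the decision scale, as section 22 and 4.4.2.1 already do. Report risk differences by stratum descriptively, since a constant relative risk implies unequal risk differences when baseline mortality differs.

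Two details need care. Section 4.4.2.1 writes its prior as uniform(1,1), which is degenerate as written; use uniform(0,1), as elsewhere. The baseline risk score has three levels, so state which contrast the rule applies to; the hypotheses in 3.8 already suggest one for 3-day risk and one for 8-day risk.

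The cost is a few sentences. It needs no new data and does not change the primary analysis.

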23 RISKS AND BENEFITS

Potential Risks

23.1.1 Unknown Risks

The primary risks to participants are due to study interventions whose human safety profile is either absent or, in most cases, early and accumulating, due to ongoing animal and/or early/first in human trials. Generally these are either still in early phase 1 testing, have not yet entered phase 1 testing, or, for those interventions in more advanced development, have not yet been tested in a human population infected with Ebola virus. Thus, unlike conventional phase 2 trials in which a safety database has already been generated to guide the dosing and schedule of study drug administration, it is presently unknown what toxicities these agents could cause when used in this critically ill patient population or, for that matter, in any humans at all.

It is anticipated that additional animal safety and toxicity studies will be in-progress at the time of trial initiation for some agents. Results will be made available to the study investigation team and pertinent regulatory bodies for review promptly, as they are available. In addition, in some cases phase 1 testing of lead candidates in normal human volunteers may commence during the same interval of time that this trial is conducted. Should it be concluded from any of these studies that there are additional significant risks to study subjects, participants will be informed and additional administration of study product may be suspended until review by the FDA as well as by each institution's IRB.

23.1.2 Risks of Phlebotomy

The primary risks of phlebotomy include local discomfort, occasional bleeding or bruising of the skin at the site of needle puncture, hematoma and, rarely, infection or fainting. Because ongoing clinical care of participants may require frequent blood draws independent of actual study-related assessments, it will be important that study teams ensure that research blood draws do not exceed the guidelines set forth by each institution's safety regulations.

23.1.3 Risks to the Study Personnel and the Environment

The principal risk for study personnel is exposure in the clinical setting to infectious pathogens from study subjects through various contact mechanisms (e.g., needlestick or mucous membrane exposure to blood borne pathogens or infected bodily fluids). Adherence to mandatory hygiene practices and infection control practices, including consistent and appropriate use of PPE, for working with patients infected with Ebola is of absolutely paramount importance throughout the conduct of this trial. Any perceived break in those practices must be reported immediately to the appropriate supervisory authorities in each institution per established algorithms.

Potential Benefits

There is no definite expectation of benefit to participants or to society at large. However, the agents likely to be investigated in this study are all thought to have some potential to offer

benefits to individual subjects, based upon previous pre-clinical and in some cases clinical investigation. Hence, while the potential benefits, if any, of a given medical intervention are presently unknown, it is conceivable that one or more interventions may subsequently be shown to offer evidence of a greater reduction in morbidity and mortality than that provided by oSOC alone. This may be manifested by a reduction in the length or the severity of disease, which may be life-saving in some cases given the nature of Ebola infection. If this is so, it is quite possible that this evidence will be suggestive, but not definitive, at this very early stage of testing. However, even if no experimental treatment intervention is shown to provide this benefit, the knowledge gained from their study will provide important information that should help better inform what role such interventions should or should not play as adjunctive treatments in managing this disease. Thus, it is possible that both positive and negative results will help inform rapidly evolving treatment paradigms, and thus may offer a societal benefit.

Alternatives

The alternative to participating in this protocol is not to participate and to receive access either to supportive care measures or to experimental therapies through other approved regulatory means.

24 RESEARCH USE OF STORED HUMAN SAMPLES, SPECIMENS, AND DATA

Intended Use of the Samples/Specimens/Data

Samples and data collected under this protocol will be used to determine the interventional agent safety, anti-viral effects, development of anti-drug antibodies, effects on immune response, and pharmacokinetics. Viral specific items of interest include: diagnostics and viral pathogenesis.

Storage of Samples/Specimens/Data

Samples obtained in this study must adhere to national regulations for long term storage. For U.S. sites, CDC regulations governing the storage of blood obtained from patients infected with Select Agents in other than BSL-4 containment facilities, which specifically require documentation of destruction of potentially infectious samples after more than 7 days' time according to established CDC guidelines. Whenever possible, sites which have access to a secure BSL-4 laboratory repository should attempt to transfer samples to that repository for longer-term storage according to approved shipping regulations applicable to select agents.

In the future, other non-protocol investigators (both at NIH and outside) may wish to study these samples and/or data. In that case, IRB approval must be sought prior to any sharing of samples. Any clinical information shared about the sample with or without patient identifiers would similarly require prior IRB approval.

The research use of stored, unlinked or unidentified samples may be exempt from the need for prospective IRB review and approval. Exemption requests will be submitted in

writing to the NIH Office of Human Subjects Research, which is authorized to determine whether a research activity is exempt.

Storage of Genetic Samples

No samples are being stored for genetic testing on the subjects.

Reporting Loss or Destruction of Samples/Specimens/Data

Any loss or unanticipated destruction of locally maintained samples (for example, due to freezer malfunction) or data (for example, misplacing a printout of data with identifiers) will be reported to the institution's IRB and to the protocol team.

